Project 3--Neuroimaging of Delirium, Leader: [name].: This study will include 3 sub-studies using magnetic resonance imaging (MRI) to characterize the functional and structural effects of delirium. In the first sub-study, multiple MRI measures, including blood flow, volumetric, and white matter damage measures, will be used to characterize the brains of 150 patients drawn from our prospective cohort, and to determine whether imaging markers can predict the risk of delirium. The second sub-study will examine all enrolled patient 12 months after the index hospitalization (or delirium episode) to identify delirium-specific risk factors and to determine the location and extent of long-term cognitive changes potentially associated with delirium. The third aim will relate imaging findings to measures derived from the other 3 projects.

Project 4--The Role of Reserve in Delirium, Leader: [name]: This study will utilize the entire cohort, as well as neuropsychological, biomarker, and neuroimaging data from Projects 1-3 to describe a comprehensive, multifaceted model for reserve. Reserve, the resilience of the brain to withstand neuropathological damage, has been extensively evaluated in dementia, but its role in delirium has remained unexplored. The goal is to develop an index for reserve, then to test whether higher reserve is independently associated with a lower rate of incident delirium and less long-term cognitive and functional decline.

Project 5-- SAGES Extension Study, Leaders: [name]: This study will collect data for the renewal application of the SAGES study. We will conduct a feasibility interview (n=100). We will recruit current SAGES participants to respond to a questionnaire regarding willingness to participate in additional studies, including a study collecting cerebral spinal fluid samples (CSF) by lumbar puncture (LP); phlebotomy to obtain blood samples; electroencephalogram (EEG); and non-invasive transcranial magnetic stimulation (TMS).

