We will also examine a non-surgical comparison group, which will be at low risk for hospitalization, and will be matched with the surgical group. Other than surgery, they will meet all other inclusion and exclusion criteria for the surgical group. The purpose of the group is to help us evaluate the cognitive trajectory in the absence of hospitalization, surgery, and delirium and to quantify retest (learning) effects. For this group, we will enroll 120 primary care patients from BIDMC, who will be frequency matched (using a prospective frequency matching algorithm) to the surgical group on age, gender, education, baseline cognitive function, and comorbidities (i.e., both vascular and nonvascular comorbidities). We have successfully implemented this type of prospective matching in our pilot work and previous studies (*Charpentier 2001*).

For Project 5, we will enroll current SAGES patients (n=100). Interim analysis of data collected from the current SAGES study has identified a need for additional biomarkers and other neurophysiologic measures to complement and further the work done thus far in SAGES. With this feasibility study we want to evaluate if SAGES participants would be willing to undergo additional procedures.

Project 6: For this project, the Fried frailty index (*Fried 2000*) will be utilized to identify contrasting aging phenotypes (frail and robust/non-frail) in the SAGES I original sample. 1. We will enroll current SAGES I participants (up to n=30) to identify 15 frail and 15 robust/non-frail individuals, and to obtain fresh blood specimens to develop iPSC cell lines (5 per participant). 2. We will utilize the iPSC cell lines

to probe various molecular-physiologic differences between the frail and non-frail samples in 4 different labs:

- a) Neurophysiology: The [name] lab will differentiate the iPS cells into neurons and probe neurophysiologic differences
 - b) Muscle function: The [name] lab will differentiate the iPS cells into muscle cells and probe physiologic differences at the molecular level
 - c) Mitochondrial function: The [name] lab will explore differences in mitochondrial functioning, applying metabolomic and other molecular approaches
 - d) Nicotinamide adenine dinucleotide (NAD) function: The [name] lab will explore differences in oxidative functioning particularly in relationship to NAD functioning.
3. We will develop and validate a human platform to further examine frailty in vitro in future larger studies

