• SF-36 general health and well-being (Ware 1992)	INT	Secondary outcome
• Rehospitalization(s)	INT, FAM, MR	Secondary outcome
• Institutionalization	INT, FAM, MR	Secondary outcome
• Death, Cause of death	FAM, MR, NDI	Secondary outcome; censoring variable

*Cognitive reserve markers include: education, occupation, income, wealth, head circumference, Cognitive Activities Scale, WHI Activities Scale; EPESE Activities. 3MS=Modified MMSE; CAM= Confusion Assessment Method; MDAS= Memorial Delirium Assessment Scale; DSI=delirium symptom interview; DRS= Dementia Rating Scale; DQ=Dementia Questionnaire; WTAR= Wechsler Test of Adult Reading; ADL = Activities of Daily Living; IADL= Instrumental Activities of Daily Living; Na=sodium; K=potassium; Glu=glucose; Hct=hematocrit; Alb=albumin; BUN/Cr= Blood urea nitrogen to creatinine ratio; APACHE=Acute Physiology, Age and Chronic Health Evaluation Form; HTN=hypertension; DM=diabetes mellitus; chol=hypercholesterolemia; VD=vascular disease; LOS=Length of hospital stay; GDS= Geriatric Depression Scale; INT= patient interview; MR= medical record abstraction; FAM=family/caregiver interview; LAB=blood testing; RN INT=nursing staff interview; NDI=National Death Index (including death certificate information).

Study Description: Part B
UB Form: 9-2015
PI Revision Date: 9-12-19

A.9. Procedures for the Project 5. Feasibility Interview:

A.9.1. Subject selection: 100 currently enrolled SAGES participants will take part in the Project 5 Feasibility Interview. Participants will be called by a SAGES team member as part of a routine study call and asked if they would be willing to participate in the Project 5 Feasibility interview during a phone call. Participants who express interest in the survey will then be consented on the phone using verbal consent procedures and the feasibility interview will be administered.

A.9.1.2 Instruments: Participants who consent to take part will be given a 20 minute phone survey using standardized questions with multiple-choice and short response questions.

A.10 Procedures for the Project 6—SAGES Harvard Initiative on Aging Pilot: Exploring Molecular Mechanisms of Frailty:

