B.1.5. Sample Size for Project 5. For the Feasibility Interview, the sample size of 100 was selected to enable robust estimates of the percent of SAGES participants willing to undergo these procedures.

B.1.6. Sample Size for Project 6. Due to budgetary constraints of generating the cell lines and running assays across 5 laboratories, we will include a convenience sample of only up to 30 orthopedic surgery participants (~15 frail and ~15 non-frail) for this pilot study.

B.2. Data Analysis.

The Data Management and Statistical Analysis (DMSA) Core (Core C) will provide data management services, statistical analyses and collaboration to the other Cores and Projects in the Program Project. The primary responsibilities of the DMSA Core will be to develop information systems and software for tracking participants, receiving, management and cleaning of data, generation of data sets, and performing statistical analyses tied to the specific aims of the projects. The specific aims for this Core are: 1. To generate information systems and software for tracking participants and flow of data; 2. To assemble and manage a database of longitudinal information collected from participants during screening, follow up and the conduct of individual projects; 3. To collaborate with the Epidemiology Core and Project Leaders in all phases of study design including determining the sampling scheme for the study, addressing non-response and providing real-time selection, enrollment, and matching as needed for substudies (Project 3); 4. To provide methodologic and analytic expertise to Project Investigators including study design and conduct, development and implementation of data analytical plans, interpretation of statistical results and manuscript preparation; 5. To lead analyses of variables collected by the Epidemiology Core and individual research projects; and 6. To develop composites for cognition and functional outcomes. Senior leadership for the Core will be provided by L. [name], Professor and former Chair of the Department of Biostatistics at Boston University School of Public Health. Day-to-day and operational leadership will be provided by [name], located at the Institute for Aging Research (IFAR) of the Hebrew Rehabilitation Center (HRC). [name] (BIDMC) will also serve as coinvestigator and member of this Core. Data will be stored and analyzed at the Hebrew Rehabilitation Center.

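### Project 5's 100 respondents are those who agree to a survey on further studies, so n = 100 secures precision among respondents, not a robust percentage for SAGES participants

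*Protocol*

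**What the plan says.** The target is stated twice. Section A.2 gives the purpose: "With this feasibility study we want to evaluate if SAGES participants would be willing to undergo additional procedures". Section B.1.5 gives the sample size rationale: "the sample size of 100 was selected to enable robust estimates of the percent of SAGES participants willing to undergo these procedures". It states no confidence level, half-width, expected percentage or agreement rate.

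Section B1 (Project 5) describes the instrument. Participants "respond to a questionnaire regarding willingness to participate in additional studies", and the studies named involve lumbar puncture for CSF, phlebotomy, EEG and TMS.

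Section A.9.1 describes how the sample is formed. The 100 are people who complete the interview: "100 currently enrolled SAGES participants will take part in the Project 5 Feasibility Interview". They are called as part of routine contact and "asked if they would be willing to participate in the Project 5 Feasibility interview during a phone call". Then: "Participants who express interest in the survey will then be consented on the phone using verbal consent procedures".

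Section B1 limits the frame to currently active participants. Section B.2 gives Project 5 a single line, promising summary and descriptive statistics. Neither section sets a denominator for the percentages or a step for recording people who decline.

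**The concern.** The quantity wanted is a percentage of SAGES participants. The quantity observed is a percentage of those who agreed to be interviewed about taking on more research. Someone with no appetite for further procedures may well also pass up the interview. If so, non-response is related to the answer and the respondents' percentage sits too high.

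The sample size argument does not help. A larger n narrows the interval around the respondents' percentage but leaves any gap between respondents and decliners where it was. Calling the estimate robust on the strength of n alone therefore claims more than the design delivers.

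At stake is the main product of Project 5, a feasibility figure meant to support the renewal application.

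**Working it through.** **Inputs from the protocol.** n = 100 respondents (A.9.1, B.1.5). The protocol gives no precision target, so 100 cannot be re-derived. Only the precision it implies can be computed.

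**Inputs that are assumed.** These are the willingness among respondents *p*, the willingness among decliners *q*, and the share of those approached who decline the interview *d*. None of them is in the protocol, so ranges are shown.

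**Step 1: implied precision.** The 95% half-width is 1.96 × √(p(1 − p)/100).

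- p = 0.5: 1.96 × √0.0025 = 9.8 points
- p = 0.6: 1.96 × √0.0024 = 9.6 points
- p = 0.7: 1.96 × √0.0021 = 9.0 points

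A finite-population correction changes little: at p = 0.5 it gives 8.9 points for N = 550 and 9.0 for N = 670.

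**Step 2: selection bias.** Willingness among all approached is p(1 − d) + qd. The respondents' figure differs from this by d(p − q), which does not contain n.

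With p = 60%:

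| Declining (d) | All approached, q = 0 | Bias | All approached, q = 30% | Bias | All approached, q = 60% | Bias |
|---|---|---|---|---|---|---|
| 10% | 54% | 6 | 57% | 3 | 60% | 0 |
| 20% | 48% | 12 | 54% | 6 | 60% | 0 |
| 30% | 42% | 18 | 51% | 9 | 60% | 0 |
| 40% | 36% | 24 | 48% | 12 | 60% | 0 |

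For example, at d = 20%, 125 people are approached to obtain 100 interviews (100/0.8). Sixty of the 100 say yes, and 60/125 = 48%.

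**Step 3: when bias exceeds sampling error.** Set d(p − q) equal to the half-width.

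- p = 60%, no decliner willing: d = 9.6/60 = 16%
- p = 60%, decliners half as willing: d = 9.6/30 = 32%
- p = 50%: d = 9.8/50, about 20%, and 9.8/25, about 39%
- p = 30%: d = 9.0/30 = 30%, and 9.0/15 = 60%

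The bias matters most for procedures that look well accepted. At p = 10% the half-width is 5.9 points, and bias reaches it only at 5.9/10 = 59% declining, even if every decliner is unwilling.

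**Step 4: direction.** The sign is not guaranteed. If decliners were 1.2 times as willing as respondents (60% against 50%), the respondents' figure would be too low: by 0.1 × 10 = 1 point at d = 10% and 0.5 × 10 = 5 points at d = 50%.

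**The case against.** Much of the case on the other side stands.

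- **A reader might infer that willingness will be overstated.** The protocol does not show this. It has no agreement rate and no information on decliners, and the bias is zero if declining reflects lack of time or fatigue. Section A.9.1 does not say that the procedures are described before interest is asked for. The request is also light: a 20-minute call (A.9.1.2), $20 (B.4.1) and participants already active in the cohort. Refusal may be low.
- **A reader might infer that decliners are struck from the denominator by rule.** No section sets a denominator, and descriptive reporting could include the number approached. The sample's definition as 100 who take part makes the respondents the natural denominator, but that is an implication.
- **A reader might infer that the renewal study will be planned at sizes the cohort cannot supply.** The protocol gives no such sizes and does not say that recruitment will be set from this percentage.
- **The 16% threshold is the extreme case.** It requires every decliner to be unwilling. If decliners are half as willing, the threshold is 32%.
- **Denominators and response rates usually belong in an analysis plan.** That is true, and their absence is not the point here. The point is the claim made in B.1.5. A later plan also cannot recover decliners who were not recorded when called.

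Section B.2 lists dealing with non-response among the data core's general duties. That shows awareness, but it sets no step for Project 5. The need for consent is likewise no fault. What remains is the mismatch between the stated target and the people sampled.

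**Conclusion.** The point holds as a risk, not as a demonstrated error. B.1.5 claims a robust estimate for SAGES participants, while A.9.1 yields one for those who agree to be surveyed. What n = 100 supports is a 95% half-width of about 9 to 10 points among respondents at 50-70% willing.

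Under the assumed 60% willing and 10-40% declining, the respondents' figure would be too high by 6 to 24 points if no decliner is willing, by 3 to 12 points if decliners are half as willing, and by nothing if declining is unrelated to willingness. The protocol does not allow a choice among these.

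The importance is minor. Project 5 is a descriptive feasibility survey, and no primary outcome or Project 1-4 analysis depends on it.

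**What to change.** 1. In A.9.1, log every participant approached on the routine call and whether they agreed to the interview.
2. Report the agreement rate. For each procedure, report the percentage willing among respondents and the percentage among all approached with decliners counted as not willing. Label the second as a lower bound for those approached.
3. Compare decliners with respondents on data already held, such as age, cognition and function.
4. Reword B.1.5 to claim precision among respondents only, and state the half-width.

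The cost is a tally on calls already being made and one further denominator, with no new participants or contacts. The drawback is that the second percentage will look less favourable in the renewal application.

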
For secondary analyses, we propose to examine the cognitive trajectory up to 36-month follow-up. Prorating the Francis estimate to 36 months, yields a net difference of -1.5 SD units for persons with delirium. A conservative estimate on statistical power can be based on the anticipated complete sample of 53 of the 500 surgical patients available at follow-up month 36 (213 are censored due to truncated follow-up; the rest due to death and other losses). Assuming a cumulative incidence of delirium of 25% and a Type-I error of 5%, we estimate that we will have 99% power to detect an effect as large as -1.5 SD units; we will have >80% power to detect effects of -0.91 SD units. Thus, despite attrition, we anticipate good power to test our secondary aims.

Sample Size for the Nonsurgical Comparison Group: The nonsurgical comparison group (N= 120) is utilized only by Projects 1 and 4. Its main purpose is to quantify normal age-related changes, and to quantify retest (learning) effects on cognitive testing over time. The sample size is justified in that with N=120, assuming a large correlation ($r=.80$) of baseline and repeat testing, and a moderate retest effect (standardized difference of 0.50 units), the probable (standard) error of the mean retest effect is about 10% of a standard deviation. This level of precision is sufficient to quantify the magnitude of retest effects, which are not a primary focus but important to define and statistically isolate from the other main effects (surgery, delirium and their interactions with longer-term decline).

Similar studies have also used samples of 120 as comparison groups

B.1.1.2 Sample Size for Project 1 Sub-study: Our goal is to enroll 240 patients with or without cognitive decline for this sub-study. For the clinical outcomes sub-study, over the next year, we anticipate a total of 256 patients will reach the 6-, 12-, or 18-month follow-up assessments. We estimate that 25-50 patients, or 10-20% of those achieving the 6-18 month follow up thresholds, will meet the above criteria and require clinical examinations over the supplement year. The 10-20% figure is considered to be a reliable estimate based on prior studies in the literature (Bickel 2008,, as well as our preliminary experience using our primary cognitive outcome, the general cognitive performance measure (GCP), where we find that of 45 study subjects who have completed 6 months of follow-up, 13% show a reliable decline in cognitive performance

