Table 3 provides a brief description of each Project's hypotheses and a general indication of the analytic approach. Projects 1-4 have hypotheses that involve change, including change in binary variables (occurrence of delirium, a non-absorbing state) or change in cognition. A general approach to the analysis of longitudinal data of this kind is the general linear mixed model (GLMM). Survival models (e.g., Cox proportional hazards, frailty, and discrete time survival models) could also be used for binary events if they are assumed to be absorbing (e.g., time to first delirium). Parameters for such models can be estimated with a variety of different software packages to yield varying classes of models used for change studies: individual growth curve models; random coefficient models; multilevel models; mixed models; or hierarchical linear models.

We will consider several approaches to account for missing data in our study, including maximum likelihood methods that model the missingness and imputation. One approach uses a random effects model for the outcome measurement, where the random effect represents the subject-specific effect. A second possible approach is the random-coefficient selection model that allows subject drop-out to depend on missing values of the outcome variable. Still another approach will be multiple imputation methods. Applying these multiple methods will allow us to assess the degree to which our inferences are robust to different methods for handling missing data. If findings are consistent across methods, we will be reassured about the robustness of our findings. If findings are not consistent, then these multiple methods allow us to further explore the inconsistency and to decide on the best approach.

Project 5 data will be analyzed using summery and descriptive statistics.

Project 6 data will be analyzed at the following 5 Harvard labs:
Neutrons: [name] lab will differentiate the iPS cells into neurons and probe neurophysiologic differences. Muscle cells: The [name] lab will differentiate the iPS cells into muscle cells and probe physiologic differences at the molecular level. Mitochondrial function: The [name] lab will explore differences in mitochondrial functioning, applying metabolomic and other molecular approaches.

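### The missing-data method may be chosen, with no stated criterion, after the candidate methods have given conflicting results

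*Protocol*

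**What the plan says.** The missing-data paragraph of section B.2 (Data Analysis) opens tentatively: "We will consider several approaches to account for missing data in our study". Three candidates follow:

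- a random-effects model for the scores, with an effect for each patient;
- a selection model, introduced in these words: "A second possible approach is the random-coefficient selection model that allows subject drop-out to depend on missing values of the outcome variable";
- multiple imputation.

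None is called primary. The reason for using several is then given: "Applying these multiple methods will allow us to assess the degree to which our inferences are robust to different methods for handling missing data". Agreement across methods is to be taken as reassurance. For disagreement the text says: "If findings are not consistent, then these multiple methods allow us to further explore the inconsistency and to decide on the best approach".

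Two other places bear on this. Table 3 assigns Project 1 Aims 1-2 a general linear mixed model, with the time-by-delirium interaction as the effect of interest. Section B.1.1 sets the type I error for the primary cognitive outcome at 5% and expects 400 of 500 surgical patients to have complete observations at 18 months.

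**The concern.** A set of sensitivity analyses has a fixed primary result, and the alternatives show how far that result depends on untestable assumptions. The paragraph in B.2 works like that only when the methods agree. When they disagree it changes role and becomes a choice among the methods, made by people who already know what each one concludes. It does not say what would make one approach best, who decides, or whether the rejected results are reported.

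The data cannot supply the missing criterion. The selection model lets drop-out depend on scores that were not observed. A standard random-effects likelihood analysis, and multiple imputation in its usual form, assume that it does not, given what was observed. Observed data cannot fully separate these positions, so a judgement of what is best made after the event rests on opinion, and that opinion is formed with the answers visible.

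At stake is the error rate of the main delirium comparison. The 5% in B.1.1 applies to one analysis fixed in advance. It does not apply to a result picked from several.

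**Working it through.** **1. The plan's own power figures (B.1.1).** Inputs: 400 complete cases, 25% with delirium (100 against 300), type I error 5%. B.1.1 does not say whether the test is one- or two-sided; I assume two-sided. Work in SD units.

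- Standard error = √(1/300 + 1/100) = 0.1155
- Power at 0.61 SD: 0.61/0.1155 − 1.96 = 3.32, giving 99.96% (plan: 100%)
- Power at 0.33 SD: 0.33/0.1155 − 1.96 = 0.90, giving 81.5% (plan: above 80%)
- Smallest effect with 80% power: (1.960 + 0.842) × 0.1155 = 0.323 SD

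The stated power reproduces. It assumes a single test at 5%.

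**2. How much of the primary comparison depends on the missing-data method.** 500 − 400 = 100 patients, or 20%, are expected to lack a full set of observations at 18 months. Many of them will still contribute some visits, so this is the number exposed to the choice of method, not the number without data.

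**3. Type I error if the method is chosen freely.** Let Z₁, Z₂, Z₃ be the test statistics from the three methods when delirium has no effect. Each is standard normal, with a common pairwise correlation r because all three use the same data. If the most favourable result is always the one reported, the error rate is

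P(max |Zᵢ| > 1.96).

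If the three were independent this would be 1 − 0.95³ = 14.3%, an upper reference that is unrealistic here. For correlated statistics, simulation with 1,000,000 draws per row gives:

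| Assumed r | Three methods | Two methods |
|---|---|---|
| 0.99 | 6.0% | 5.6% |
| 0.95 | 7.4% | 6.5% |
| 0.90 | 8.4% | 7.0% |
| 0.80 | 9.8% | 7.8% |

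The protocol gives no correlation, so r is an assumption and the range is the result. The two-method column covers the possibility that only two candidates are carried through, since B.2 words all of them tentatively.

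**4. With one method fixed in advance.** The error rate returns to 5%, and the power in step 1 is unchanged.

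**The case against.** The strongest reply is that B.2 describes a robustness check and says so. The outcome model and the effect for Project 1 Aims 1-2 are set in Table 3, the open choice arises only if the methods disagree, and the team undertakes to explore a disagreement before deciding. Best need not mean most significant, and a statistical analysis plan not seen here may name a primary method.

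Much of this stands. It rules out saying that the primary inference is results-driven as a matter of course; the exposure is conditional on disagreement. It also makes the figures above a ceiling under assumed correlations, because nothing in the protocol says the most favourable result will be picked.

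It does not remove the point. Table 3 fixes the model family but not the treatment of missing scores, and B.2 presents the table as a broad outline only. An analysis plan that named one method and held to it would contradict the sentence in B.2, so that sentence needs correcting either way.

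A reader might go further and infer that deaths are handled as ordinary drop-out, so that cognition is modelled or imputed for patients who have died. Table 2 labels death "Secondary outcome; censoring variable", and the 36-month calculation in B.1.1 groups patients missing for reasons other than truncated follow-up as "the rest due to death and other losses". The protocol does not support that inference. No section says scores will be created after death. Section A.2 ends a patient's follow-up at death, and a censoring label marks where observation stops. How death enters the model can properly be left to the analysis plan. The 36-month losses belong to a secondary analysis and do not separate deaths from other losses, so they say nothing about the size of this problem at 18 months.

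**Conclusion.** The point holds in a limited form. Section B.2 contains a written rule under which the missing-data method can be settled after conflicting results are seen, with no criterion. The nominal 5% is therefore not protected when the methods disagree.

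The worst-case size is a type I error of about 6% to 10% instead of 5%. It rests on three assumptions: three methods are run, the most favourable is always the one reported, and the between-method correlation lies between 0.99 and 0.80. Methods that track each other very closely would put it near the lower end; a choice made on principle would put it lower still. The rule can reach the primary 18-month outcome, where about 20% of patients are expected to be incomplete. The stated power is not affected. This is worth correcting before analysis, and it does not undermine the design.

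**What to change.** Replace the sentence on inconsistent findings in section B.2 with:

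> *The likelihood-based mixed model is the primary analysis. The selection model and multiple imputation are sensitivity analyses, reported whatever they show. Disagreement between them is reported as uncertainty and does not change the primary method.*

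This agrees with the model already assigned to Project 1 Aims 1-2 in Table 3. Any separate analysis plan should say the same.

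The cost is one sentence of wording. No new data, extra analysis or change in sample size is needed. The real downside is that the team gives up the freedom to switch methods if it later comes to prefer another set of missing-data assumptions. It can still argue that case openly from the reported sensitivity analyses.
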